8.8 CSF, Serum and Plasma Sub-study Assessments

CSF, serum and plasma will be taken at screening within 14 days prior to first dose of study drug and within 14 days prior to weeks 24 and 48 to measure biomarkers (e.g., AB42, AB42/40 ratio, total tau, p-tau-181, neurogranin, NfL, YKL-40, VILIP, SNAP-25, sTREM2, GFAP) in the double-blind treatment phase of the trial. For the OLE phase, serum and plasma will be taken at weeks 24 and 48. These samples will be banked at a central biorepository for future exploratory biomarker analyses.

CSF samples should be collected at the same time of day, either morning (between 8 and 10AM) or afternoon (between 1 and 3PM). The first lumbar puncture must be conducted prior to initiation of study drug. Plasma samples for PK should be drawn at the time of lumbar puncture. Date and time of doses on the day of lumbar puncture and day prior should be collected in case report forms, for entry into the EDC system.

The estimated 100 participants (n=50 active, n=50 placebo) who are within the sentinel cohort of the double-blind treatment phase of the trial will constitute the study sample for the columns and will also have the opportunity to participate in a CSF, serum, and plasma sub-study, with samples drawn in the screening period and at week 24, with the option for a third sampling timepoint at week 48

In addition to the sentinel sub-study participants, other consenting trial participants will be approached to undergo a blood draw to provide serum and plasma biomarkers. For CSF, consenting participants will undergo a lumbar puncture at screening within 14 days prior to first dose of study drug and within 14 days prior to week 48 to measure the CSF biomarkers in the double-blind treatment phase of the trial.

Anti-platelet and anticoagulant medications and lumbar puncture are addressed above in in (Prohibited Concomitant Medications, Section 7.4.2). Participants who are taking anticoagulants or dual antiplatelet drugs are excluded from the CSF sub-study.

Details of the CSF sampling are contained in the Study Procedures Manual.

The unused portion of CSF may be transferred to the National Cell Repository for Alzheimer's Disease (NCRAD) for future research. Participants will be given the choice to allow such sample retention and further investigation of their CSF.

9 STUDY-SPECIFIC INSTRUMENTS

9.1 Cognitive Measures

9.1.1 Alzheimer's Disease Assessment Scale Cognitive Subscale (ADAS-Cog 11)

The ADAS-Cog 11 (Rosen, Mohs, & Davis, 1984) is a structured scale that evaluates memory (word recall, word recognition), reasoning (following commands), language (naming, comprehension), orientation, ideational praxis (placing a letter in an envelope) and constructional praxis (copying geometric designs). Ratings of spoken language, language comprehension, word finding difficulty, and ability to remember test instructions are also obtained. The test is scored in terms of errors, with higher scores reflecting poorer performance and greater impairment. Scores can range from 0 (best) to 70 (worse).

9.1.2 Mini-Mental State Examination (MMSE)

The MMSE is a frequently used screening instrument for Alzheimer's disease drug trials. It evaluates orientation, memory, attention, concentration, naming, repetition, comprehension, and ability to create a sentence and to copy two intersecting pentagons (Folstein, Folstein, & McHugh, 1975). A lower score indicates more cognitive impairment. The highest (best) score is 30.

9.1.3 Montreal Cognitive Assessment (MoCA)

The MoCA is a brief mental status exam which was designed to be more sensitive to mild cognitive impairment and early dementia than the MMSE (Nasreddine et al., 2005). It assesses numerous cognitive domains, including attention and concentration, executive functions, memory, language, visuoconstructional skills, conceptual thinking, calculations, and orientation. Like the MMSE, the highest (best) score is 30. Administering both the MoCA and the MMSE in this trial will allow comparisons of the utility within the setting of a clinical trial.

9.1.4 Neuropsychological Test Battery (NTB)

The neuropsychological battery from the Uniform Data Set (v3.0 – Form C2) of the National Alzheimer's Coordinating Center (NACC) (Weintraub et al., 2009) will be administered to provide a more detailed assessment of cognition. The battery includes brief measures of attention, processing speed, executive function, episodic memory, and language. Exploratory analyses will evaluate the treatment effects on a composite measure of this neuropsychological battery between baseline and endpoint . As described in the manual for test administration and scoring (Version 3.0, March 2015), Form C2 of the NACC UDS battery includes the following measures:

9.1.4.1 Craft Story 21 Recall (Immediate and Delayed)

This is a measure of verbal episodic memory (Craft et al., 1996). A brief story is read to the participant, who is then asked to retell it immediately from memory. The primary measure of performance is the number of story units recalled. Delayed recall of the story is assessed 20 minutes after immediate recall. Other neuropsychological measures are administered during the delay interval (Range: 0-25 for each recall trial).

9.1.4.2 Benson Complex Figure Copy & Recall

This test is a simplified form of the Rey-Osterrieth Complex Figure (Possin, Laluz, Alcantar, Miller, & Kramer, 2011). The purpose is to assess visuoconstructional and visual memory functions. In this test, the participant is presented with a figure composed of geometric shapes. The participant is then asked to reproduce (i.e., copy) the figure on the same page. The accuracy of each shape and its placement are recorded. The primary measure of performance is the total score for copying the figure (Range: 0-17). Approximately 10-15 minutes after the participant copies the figure, visual memory is assessed by asking the participant to draw the figure again, from memory, on a blank page. The accuracy of each shape and its placement are recorded. The primary measure of performance is the total score for the delayed drawing of the Benson figure (Range: 0-17).

9.1.4.3 Multilingual Naming Test (MINT)

The MINT is a test of visual confrontation naming (Ivanova, Salmon, & Gollan, 2013). Participants are required to identify (i.e., name) line drawings of objects. If the initial response is incorrect, semantic and/or phonemic cues are provided, as appropriate. Items are counted as correct if spontaneously named after semantic cuing (Range: 0-32).

9.1.4.4 Trail Making Test (Trails A and B)

The Trail Making Test is a test of processing speed and executive function. Trails A consists of 25 circles numbered 1 through 25 distributed over a white sheet of paper. The participant is instructed to draw a line to connect the circles in ascending numerical order as quickly as possible (150 second maximum). Trails B consists of 25 circles containing either numbers (1 through 13) or letters (A through L) that are randomly distributed across the page, and participants are instructed to connect the circles in alternating and ascending order (e.g., 1 to A; 2 to B). Performance is judged in terms of time to complete each trial. Time to complete Trails B (300 second maximum),

adjusted for the time taken to complete Trails A to control for sensorimotor demands of the task, is a sensitive measure of executive function and working memory.

9.1.4.5 *Verbal Fluency – Category Fluency*

Category fluency assesses semantic memory and language fluency in which participants name as many different exemplars of a given semantic category as rapidly as possible. Participants will be given 60 seconds to name exemplars in each of two categories: animals and vegetables.

9.1.4.6 *Verbal Fluency – Phonemic Fluency*

Phonemic Fluency is a measure of word generation that may be sensitive to dysfunction in the dominant frontal lobe. Participants will be given 60 seconds to name exemplars that begin with each of the two letters: F and L.

9.1.4.7 Number Span Forward and Backward

Number Span assesses two different working memory constructs: Forward Number Span measures the capacity for retaining information very briefly for the purpose of repeating it exactly, while Backward Number Span measures the ability not only to retain the information but also to mentally manipulate the numbers and recite them in reverse sequence. Numbers for both forward and backward span tests are presented with sequences ranging from 2 to 9 numbers. Two trials are administered at each sequence length. Two scores are reported for each task: number of correct trials and longest sequence repeated correctly prior to failing two consecutive trials of the same length.

9.2 Behavioral and Functional Measures

9.2.1 Clinical Dementia Rating (CDR) Scale – Sum of Boxes (SOB)

The CDR-SOB (Hughes, Berg, Danziger, Coben, & Martin, 1982) is a validated composite rating of cognition and everyday functioning used in longitudinal AD research which incorporates both informant input and direct assessment of performance. It assesses through semi structured interview 3 cognitive domains including memory, orientation, and judgement/problem solving and 3 everyday functional domains including community affairs, home and hobbies and personal care. There are 5 levels of impairment from none CDR=0 to severe CDR=3. The individual domain scores are added to create a sum of the box scores.

9.2.2 ADCS-Activities of Daily Living (ADCS-ADL) Scale

The ADCS-ADL scale is a questionnaire developed by the ADCS to assess functional performance in participants with AD (Galasko et al., 1997). Scores range from 0 to 75, with higher scores indicating better function.

9.2.3 Neuropsychiatric Inventory (NPI)

The NPI is a well-validated, reliable, multi-item instrument to assess psychopathology in AD dementia based on the results of an interview with the study partner (Cummings, 1997). The NPI evaluates both the frequency and severity of 10 neuropsychiatric features, including delusions, hallucinations, agitation/aggression, dysphoria, anxiety, euphoria, apathy, disinhibition, irritability and lability, and aberrant motor behavior, as well as evaluates sleep and appetite/eating disorders. Frequency assessments range from 1 (occasionally, less than once per week) to 4 (very frequently, once or more per day or continuously). Severity assessments range from 1 (mild) to 3 (severe). The score for each subscale is the product of severity and frequency and the total score is the sum of all subscales.

9.3 Modified Hachinski

This brief questionnaire, conducted by a clinician, incorporates information regarding medical history, cognitive symptoms and features of stroke, reported by a study partner as well as the neurological examination, and neuroimaging studies (Rosen, Terry, Fuld, Katzman, & Peck, 1980).

9.4 Sheehan Suicidality Tracking Scale (Sheehan STS)

The Sheehan STS (S-STS) is a prospective, participant self-reported or clinician administered rating scale that contains 16 questions to track both treatment-emergent suicidal ideation and behaviors (Sheehan, Alphs, et al., 2014; Sheehan, Giddens, & Sheehan, 2014). The S-STS will be completed on a paper form at the site. At the screening visit, the recall period for completing the S-STS is 12 months prior; at all other visits, the recall period for completing the S-STS is since the last visit. Subjects who have an S-STS score > 0 should be evaluated by the investigator. If the investigator determines that a subject is at risk of suicide or self-harm, appropriate measures to ensure the subject's safety and obtain mental health evaluation must be implemented. The subject must immediately be discontinued from the study. The event should be recorded as either an AE or SAE as determined by the investigator and reported within 24 hours to the Sponsor.

9.5 Research Satisfaction Survey

A Research Satisfaction Survey will be administered to the participant and study partner to evaluate satisfaction with the study. The survey may reveal specific aspects of the study that participants dislike, which can inform efforts to improve their experiences when participating in future studies. Past studies show that participant input and feedback is important for retention (Miller, Duncan, Sorrell, & Brown, 2005).

9.6 Treatment Blinding Questionnaire

Following the week 48 clinic assessment, the site Investigator and Raters will each complete a Treatment Blinding Questionnaire to document knowledge of intervention group assignment per participant.

10 EARLY DISCONTINUATION/WITHDRAWAL PROCEDURES

The entire study may be discontinued at the discretion of ADCS or Biohaven. In these circumstances the Investigator will arrange for all ongoing participants to be seen and for their study medication to be discontinued as soon as is safely possible.

Participants are free to withdraw from study participation at any time, for any reason, and without prejudice.

Discontinuation of study treatment and/or the participation of an individual participant in the study will be terminated in the following circumstances:

- Withdrawal of informed consent by the participant or LAR. If the study partner withdraws
 his/her consent to participate then attempts will be made to find a replacement. In any event
 the participant will be continued in the study in so far as possible. Participants who
 withdraw consent will be advised by the Investigator regarding subsequent treatment and
 investigation.
- Treatment of a participant with a non-permitted concomitant medication may necessitate discontinuation from study medications, and will be determined by the Investigator in conjunction with the Medical Monitor.
- Adverse event or other significant medical condition which, in the opinion of the Investigator render it necessary to discontinue study medication.
- The participant experiences a medical emergency that necessitates unblinding their treatment assignment. (See Section 6.6).
- Any other occurrence that, in the Investigator's opinion, makes continued participation contrary to the participant's best interests.
- Movement of participant into a long-term care nursing facility. Movement into an assisted living facility is not cause for discontinuation from the study.

Participants who discontinue active treatment for any reason will have the opportunity to continue on the protocol with further visits per protocol to the end of the double-blind phase of the study with their ongoing consent. Their continued participation will be encouraged.

The Investigators at each site will make every reasonable effort to maximize participant retention, even if the study treatment is discontinued before week 48. However, if an investigator removes a participant from study, or if a participant declines all further study participation during the study, an Early Termination Visit will be completed as close as possible to the time of study discontinuation. The Early Termination Visit may contain the same assessments as week 48, to allow collection of the main outcome measures. For further detail please refer to the Procedures Manual.

11 DEFINITION OF ADVERSE EVENTS

An adverse event (AE) or adverse experience is any untoward medical occurrence in a study participant who is administered a medicinal product, that does not necessarily have a causal relationship with the study treatment, and that occurs after informed consent is signed and up to 30 days after the study drug has been discontinued. An AE can therefore be any unfavorable and unintended sign, symptom, or disease temporally associated with the use of a medicinal product, whether or not considered related to the medicinal product. Pre-existing conditions, which increase in frequency or severity or worsen in nature during, or as a consequence of, use of a drug in human clinical trials, will also be considered adverse experiences. Adverse events may also include pre- or post- treatment complications that occur as a result of protocol-mandated procedures (e.g. invasive procedures such as biopsies).

An AE does not include:

- Medical or surgical procedures (e.g., surgery, endoscopy, tooth extraction, transfusion).
 The condition that leads to the procedure is the AE.
- Situations where an untoward medical occurrence has not occurred (e.g., hospitalization for elective surgery, social and/or convenience admissions).
- Worsening of symptoms associated with expected decline in Alzheimer's disease is not considered an adverse event in this study.
- Overdose of either study drug or concomitant medication without any signs or symptoms unless the participant is hospitalized for observation. Overdoses should be reported as outlined in Section 11.4.

A treatment emergent adverse event (TEAE) is defined as any AE that developed, worsened, or became serious after first dose of study drug and prior to 30 days after the last dose of study drug.

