11.1 Evaluation and Reporting of Adverse Events

All AEs (i.e., a new event or an exacerbation of a pre-existing condition) that occur from the time informed consent is signed and up to 30 days after the study drug has been discontinued must be recorded as an AE on the AE eCRF. The Investigator must follow all AEs until the AE resolves, or until the Investigator and/or the Medical Monitor determine the event is chronic or clinically stable. If an AE remains unresolved at the conclusion of the study, the Investigator and Medical Monitor will make a clinical assessment to determine whether continued follow-up of the AE is warranted. All participants who have received at least one exposure to study therapy will be evaluated for safety of study treatment.

The Investigator should attempt to establish a diagnosis of the event based on signs, symptoms and/or other clinical information. In such cases, the diagnosis should be documented as the AE and not the individual signs/symptoms.

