11.3 Collection and Reporting of Serious Adverse Events

Following written consent to participate in the study, all SAEs, whether related or not related to study drug, must be collected, including those thought to be associated with protocol-specific procedures. The reporting period ends 30 days after discontinuation of dosing. In addition, the investigator should report any SAE occurring after this time period that is believed to be related to study drug or protocol-specific procedures. Serious adverse events that occur prior to initiation of study drug will be documented in the EDC as medical history, but will still need to be reported to on an SAE form as described below.

An SAE is an AE from this study that results in any of the following outcomes:

- Death
- Life-threatening situation (participant is at immediate risk of death)
- Inpatient hospitalization or prolongation of existing hospitalization
- Persistent or significant disability/incapacity
- Congenital anomaly/birth defect in the offspring of a participant who received study drug

Considered significant by the investigator for any other reason

An SAE report should be completed for any event where doubt exists regarding its status of seriousness.

If the investigator believes that an SAE is not related to the study drug, but is potentially related to the conditions of the study (such as a withdrawal of previous therapy or a complication related to study procedure), the relationship should be specified in the narrative section of the SAE Report Form.

SAEs, whether related or not related to study drug, overdose, and potential drug induced liver injury must be reported within 24 hours of the Investigator becoming aware of the event. For this study we will be capturing SAEs through both the ADCS Electronic Data Capture (EDC) system and on an SAE report form provided by CCI In addition, all applicable SAEs must be reported by the Site Investigator to the Institutional Review Board (IRB) of record according to IRB's reporting requirements for such events.

The Site Investigator is responsible for reporting all SAEs and all Other Important Medical Events to via telephone, immediately or no later than 24 hours after awareness of the event. A representative will then immediately notify the Biohaven Medical Monitor. An SAE form must then be submitted to via the fax number indicated below.

Safety Hotline Number for SAE telephone reports:

North America: PPD

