Facsimile (fax) number for SAE report forms, to be sent within 24 hours after awareness of the event:

North America: PPD

The Site Investigator, or designated staff, is also responsible for entering the SAE information in the ADCS Electronic Data Capture (EDC) system (i.e., event term, start stop dates, causality, and severity) according to study-specific eCRF Completion Guidelines. The ADCS Medical Monitor and ADCS Project Director will be automatically notified via email upon entry of an SAE into the ADCS EDC system. A member of the ADCS Medical Safety team will inform the DSMB of the occurrence of any SAEs within 7 days of being reported. The DSMB may at any time request additional information from the ADCS in relation to a reported event.

If only limited information is initially available, follow-up reports are required. If an ongoing SAE changes in its intensity or relationship to study drug or if new information becomes available, a follow-up SAE report should be sent to within 24 hours of the Investigator becoming aware of the updated information using the same procedure used for the transmission of the initial SAE and the same event term should be used. In addition, new or revised event information must be entered into the ADCS EDC at the same time.

All SAEs should be followed to resolution or stabilization. For any questions relating to SAEs, please contact the ADCS Medical Monitor via telephone or email at the number listed on the protocol face page.

Suspected Unexpected Serious Adverse Reactions

Suspected unexpected serious adverse reactions (SUSARs) are serious adverse events that are not listed in the Investigator's Brochure as an expected AE and that the Investigator assesses as possibly related or probably related or definitely related to study drug or study procedure. United States 21 CFR 312.32 and European Union Clinical Trial Directive 2001/20/EC and the associated detailed guidance or national regulatory requirements in participating countries require the reporting of SUSARs to regulatory authorities. As the clinical trial sponsor, Biohaven is responsible for, and has procedures consistent with regulations that will be followed for, expedited reporting of SUSARs.

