#### 4.5 Planned Analyses

DSMB analyses of safety data will be performed quarterly throughout the trial period by an unblinded safety ADCS biostatistician who is not involved in the final study analysis. The quarterly analyses include an Executive Summary and a Study Summary (extracted from the protocol). These summaries are followed by tables and figures detailing elements of the current data base related to safety, specifically: Screening and Enrollment, Enrollment by MMSE, Enrollment by Month, Enrollment by Site, Inclusion and Exclusion, Screen Failure by Inclusion Criteria, Screen Failure by Exclusion Criteria, Early Discontinuation, Protocol Deviations, Demographics and Baseline Outcomes, Vital Signs, Safety, Adverse Events with Onset Prior to Randomization, Adverse Events with Onset Following Randomization, Adverse Events by Severity, AE by relatedness, Adverse Events summarized by MedDRA SOC–PT, Serious Adverse Events, and Safety Labs.

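### The adverse event definition excludes worsening put down to expected Alzheimer's decline, with no exception for serious events, so hospitalisations attributed to decline are not reliably captured as SAEs

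*Protocol*

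**What the plan says.** Protocol Section 11 lists what is not an AE. One item reads "Worsening of symptoms associated with expected decline in Alzheimer's disease is not considered an adverse event in this study". The next item excludes symptom-free overdose, "unless the participant is hospitalized for observation". Earlier in the section, the AE definition takes in "Pre-existing conditions, which increase in frequency or severity or worsen in nature during" the use of a drug in a trial. Section 11.1 tells sites to record every AE, described as "a new event or an exacerbation of a pre-existing condition".

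Section 11.3 builds on this definition: "An SAE is an AE from this study that results in any of the following outcomes". It adds that "An SAE report should be completed for any event where doubt exists regarding its status of seriousness". The coordinating centre's safety staff are to "inform the DSMB of the occurrence of any SAEs within 7 days of being reported".

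SAP Section 4.10.2 tabulates treatment-emergent SAEs and treatment-emergent AEs that lead to stopping study treatment. SAP Section 4.10.9 requires narratives for SAEs and for drug stops due to AEs. SAP Section 4.5 describes the quarterly DSMB report as "tables and figures detailing elements of the current data base related to safety" and then itemises it. The items include AE and SAE tables and one on early discontinuation.

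**The concern.** All participants have Alzheimer's disease, so some rule is needed to stop ordinary progression from filling the AE database. The difficulty is that this rule applies before anything is recorded and has no limit for seriousness. An investigator who judges that an admission for agitation or confusion reflects expected decline may properly conclude that there is no AE, and hence no SAE.

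The study drug acts on the central nervous system. In the earlier 8-week study at 140 mg, Protocol Section 1.7.1.1 reports dizziness in 11.27% against 1.43% on placebo and falls in 7.04% against 1.43%. Section 1.7.1.2 lists somnolence and vertigo among the dose-related effects of riluzole. Some drug-related confusion or loss of function could plausibly be read as disease. What is at stake is whether serious events of that kind are recorded at all, so that they can be compared between arms and seen by the DSMB.

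**Working it through.** No alpha, power or sample-size figure in the plan bears on this point. The check is to follow one event through the text: a hospitalisation that the investigator attributes to expected decline.

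1. **Is it an AE?** Under the Alzheimer's item in Section 11, no. Under the pre-existing-condition sentence in Section 11 and the recording rule in Section 11.1, arguably yes, since the disease pre-exists in every participant. Nothing says which rule prevails or how to recognise expected decline.

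2. **Does seriousness bring it back?** Not in the Alzheimer's item. The overdose item shows that the authors wrote a hospitalisation exception where they wanted one.

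3. **Can it be an SAE?** Section 11.3 requires an AE with a serious outcome. An event excluded at step 1 does not qualify. The sentence on doubt concerns whether an event is serious, and here seriousness is not in doubt.

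4. **What follows from that status?**

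| Output | Depends on AE or SAE status? |
|---|---|
| SAE form and 24-hour report (Protocol 11.3) | Yes |
| Seven-day DSMB notice (Protocol 11.3) | Yes |
| SAE table (SAP 4.10.2) | Yes |
| SAE narratives (SAP 4.10.9) | Yes |
| Table and narratives of AE-related drug stops (SAP 4.10.2, 4.10.9) | Yes |
| Early discontinuation item in the DSMB report (SAP 4.5) | No |
| Disposition table with withdrawal reasons (SAP 4.6) | No |
| Kaplan-Meier plot of time on study drug (SAP 4.10.1) | No |
| Deaths as a separate safety measure (Protocol 4.2.2) | No |

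The first four rows are where a hospitalisation would be counted, and all depend on AE or SAE status. Drug stops do have routes that do not depend on it. Those routes are weaker. SAP 4.5 does not say whether its item covers participants who stop drug but stay in the study, which Protocol Section 10 allows, or whether reasons are shown. SAP 4.6 concerns withdrawal from the phase. The exposure plot gives no reasons.

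5. **How many events?** The documents give no rate. As an illustration only, with 336 / 2 = 168 per arm:

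- assumed 1% per arm: 0.01 × 168 = 1.7 participants
- assumed 3% per arm: 0.03 × 168 = 5.0 participants
- assumed 5% per arm: 0.05 × 168 = 8.4 participants

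These are the participants per arm who would be missing from the SAE table if every such event were attributed to expected decline.

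**The case against.** The strongest reply is that the exclusion is narrow. It covers only expected decline, and an acute admission for confusion is not plainly expected. Read with the pre-existing-condition sentences, a careful investigator would report it. This stands in part: the exclusion does not remove all worsening of Alzheimer's disease. But the outcome then depends on how each investigator resolves an undefined term against two conflicting rules.

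A second reply is that other channels exist. Section 11.3 also asks for telephone reports of Other Important Medical Events. Section 14 lets the DSMB choose the content of its reports, with details in a charter that is not among these documents. Cognition and function are compared by randomised arm on ADAS-Cog and CDR-SOB at weeks 12, 24, 36 and 48, and on ADCS-ADL and NPI at weeks 24 and 48, with two-sided tests. These points carry weight against any claim that the DSMB is blind to such harm. They do not close the gap: the important-event class is undefined, and mean scores at scheduled visits do not identify hospitalisations.

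Third, a reader might infer that drug stops attributed to decline vanish from DSMB reporting. The documents do not support this, because the quarterly report has an early discontinuation item and the SAP tabulates withdrawals with reasons.

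Fourth, a reader might infer that the harm comparison is pulled toward no difference. That would follow if drug-caused events were classed as decline. But attribution is made blind, and removing true disease events removes background noise. The dizziness, fatigue and falls in the earlier study were reported as AEs, and nothing in Section 11 reclassifies them. The documents do not settle the net direction.

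**Conclusion.** The point holds as a gap in capture and a conflict in the text. Followed as written, Sections 11 and 11.3 allow a hospitalisation attributed to expected decline to go unrecorded as an SAE, and no other place in the two documents reliably counts it. Drug stops attributed to decline leave the AE-based table and narratives but remain visible, with less detail, through disposition and exposure. Deaths are listed separately.

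The size is unknown. The 2 to 8 participants per arm rest on assumed rates of 1% to 5% and on every event being attributed to decline. No particular count and no direction of bias can be claimed from the documents. The conclusion rests on the wording alone. It would weaken if the DSMB charter or site instructions, which are not available here, already required such events to be reported. The change is worth making because it is cheap and concerns serious events.

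**What to change.** Reconcile Sections 11, 11.1 and 11.3 by limiting the exclusion. Suggested wording: *AD symptom worsening in line with expected decline is not an AE unless it meets a seriousness criterion in Section 11.3 or is the reason study drug is stopped; in either case it is recorded as an AE or SAE whatever its attribution.* This is a recording rule and does not change who stops treatment. Causality can still be graded afterwards under Section 11.2.

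Add an eCRF flag for these events, so that the SAE and discontinuation tables in SAP 4.10.2 can be shown by arm with and without them.

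Do not extend the rule to every Alzheimer's-related withdrawal from the study. That would turn progression-related withdrawals and moves to a nursing facility, which Section 10 lists as a reason in its own right, into AEs.

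The cost is one sentence, one flag, a few more SAE forms, and some disease-related background events in both arms, which the flag allows to be separated.
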